# 9.10.5. Medical History

A complete medical history (e.g., per patient report) that includes all medical history within the past 5 years must be collected. Medical history will be recorded as indicated in Table 5.

### 9.10.6. Height

Height should be measured without footwear or prosthetics as indicated in Table 5.

### 9.10.7. Weight and Body Mass Index (BMI)

Weight must be measured as indicated in Table 5. BMI will be calculated in the eCRF each time the weight is recorded. The Sponsor will provide each patient with a scale to use at home to measure weight, and a diary will be provided to record the at-home weight measurements. Weights recorded in patient diaries will not be entered in the eCRF. Weights should be taken at the same time each day and recorded in a patient diary. During the first eight weeks, weights will be recorded daily; weekly weights will be recorded thereafter. Patients will be instructed to stop administering study drug and contact the investigator if their daily weight increases during the first 8 weeks per the criteria outlined in Section 9.1.1. Patients will be provided instructions

within the Informed Consent Form to help ensure consistent weight collection throughout the study.

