## 9.1.1. Management of Fluid Status

Specific risk mitigation procedures will be employed to reduce the potential for bardoxolone methyl-induced fluid overload. These procedures include exclusion of patients with any severe renal disease, defined as an eGFR value of < 30 mL/min/1.73 m^2. To exclude patients with significant cardiac dysfunction, the study will exclude patients with a history of left-sided heart disease. Patients who have evidence of volume overload at baseline, defined as BNP level of > 200 pg/mL, will also be excluded.

Laboratory data will also be used to monitor fluid status after randomization. Patients that experience a BNP > 100 pg/mL that represents a doubling (or more) of BNP levels from Day 1 should be instructed to stop taking their study medication immediately and return to the clinic within 1 week (± 3 days) for an unscheduled physical examination and laboratory assessment by the investigator.

Additionally, after randomization patients will be closely monitored for rapid weight gain suggestive of fluid overload. Patients will be given a Sponsor-provided scale to use at home to collect and record their weights daily during the first 8 weeks of the treatment period and weekly thereafter. Patients who experience a five-pound (2.3 kilogram) or greater increase in weight since their Day 1 weight during the first 8 weeks will be instructed to stop taking their study medication immediately and return to the clinic for an unscheduled physical examination and laboratory assessment by the investigator.

Investigators are encouraged to start or increase doses of diuretics (thiazides, loop diuretics) early after recognition of edema. This can be done concurrently with temporary drug discontinuation and re-initiation. Patients may not restart their study medication until the investigator has completed and documented an assessment of fluid overload.

Patients who experience a five-pound (2.3 kilogram) or greater increase in weight after the Week 8 study visit will be instructed to return to the clinic for an unscheduled physical examination and laboratory assessment by the investigator. Study medication should not be discontinued until the investigator has completed and documented an assessment of fluid overload.

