### 9.7. Unscheduled Visits

Unscheduled visits are allowed for the following reasons:

- Assessment of weight gain per Section 9.1.1;
- Management of an AE or SAE;
- Performance of additional laboratory tests for clinically abnormal laboratory test values or to confirm a possible pregnancy;
- Dose re-escalation;
- Dose de-escalation;
- Any time the investigator feels that it is clinically appropriate for patient safety.

At a minimum, unscheduled visits should include collection of AEs, clinical chemistry, hematology, concomitant medications and vital signs, as well as collection/review of weight diary. Additional conversations may be necessary with the medical monitor following an unscheduled visit to assess patient safety.

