### 9.10.10. Vital Sign Measurements

Vital sign measurements include the patient's heart rate (beats/minute taken for at least 15 seconds), respiration rate, and body temperature. Blood pressure should be taken after the patient has rested in a sitting position for at least 5 minutes. The same arm (usually the non-dominant arm) and the appropriate size cuff should be used for each measurement. Vital sign measurements should be taken as indicated in Table 5.

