12.4. Body Weight

Descriptive statistics for body weight that are collected on the eCRF and change from baseline values will be summarized by time point for each rare CKD cohort. In addition, number and percentage of patients who experience a five-pound (2.3 kilogram) or greater increase in weight will be summarized by time point. Boxplot and line graphs of change from baseline over time for weight will be plotted. Summary tables for body weight will be repeated for the following subgroups:

- Weight change will also be summarized by baseline BMI (>30 and ≤ 30 kg/m²), and
- Baseline age (>18 and ≤ 18).

12.5. 12-lead ECG

Electrocardiogram (ECG) data, such as clinical interpretation of ECGs, ventricular rate and interval assessments of PR, QRS, QT, and QTcF, will be collected on the eCRF. Descriptive statistics for observed values and change from baseline at each time point will be presented for these 12-lead ECG interval assessments by rare CKD cohort. In addition, number and percentage of patients with any abnormal values (i.e., above a pre-specified threshold) will be summarized by time point and overall while on study drug. The pre-specified levels of ECG QTc thresholds are consistent with FDA guidance.

Table 9: Pre-Specified Threshold Levels for ECG Parameters

ECG Parameter	Pre-Specified Level
PR	>200 msec
QTcF	>450 , >480 or >500 msec >30 or >60 msec increase from baseline
Heart rate	<40 , >100 beats/min

Any results that exceed the above levels (provided in the above table) will be flagged in the listing.

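### SAP 12.4 cannot identify patients whose 2.3 kg weight trigger was seen only on home weights between scheduled clinic weights, so its count will tend to understate how often the trigger was met

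*Protocol*

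**What the plan says.** **The rule.** Protocol 9.1.1 applies to "Patients who experience a five-pound (2.3 kilogram) or greater increase in weight since their Day 1 weight during the first 8 weeks". They are told to stop study drug at once and to "return to the clinic for an unscheduled physical examination and laboratory assessment by the investigator".

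**The measurement.** Protocol 9.10.7 supplies a home scale and diary: "During the first eight weeks, weights will be recorded daily; weekly weights will be recorded thereafter". Patients are to stop drug themselves and contact the investigator when the 9.1.1 criterion is met. The section also states "Weights recorded in patient diaries will not be entered in the eCRF".

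**The triggered visit.** Protocol 9.7 sets the minimum: "At a minimum, unscheduled visits should include collection of AEs, clinical chemistry, hematology, concomitant medications and vital signs", together with collection or review of the weight diary. A clinic weight is not named. The vital signs in Protocol 9.10.10 are heart rate, "respiration rate, and body temperature", with blood pressure. The examination in 9.10.11 lists body systems and does not mention weight.

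**The analysis.** SAP 12.4 plans "Descriptive statistics for body weight that are collected on the eCRF" and, by time point, the number and percentage of patients with a gain of 2.3 kg or more. SAP 7 keeps unscheduled and repeat measurements out of summary tables unless otherwise specified.

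**The concern.** SAP 12.4 uses the same 2.3 kg threshold as the stop rule, so its table will naturally be read as the frequency of the trial's own fluid-overload signal. It is built from a different and much sparser series of weights than the one patients act on.

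Safety is a primary objective (Protocol 6.1). Protocol 5.1.2.1 reports that fluid overload and heart failure hospitalizations were increased in the Phase 3 trial in Stage 4 CKD, mainly in the first three to four weeks, and that heart failure was often preceded by rapid weight gain. The trial has no control arm against which incomplete capture could be judged. A patient who gains 2.3 kg at home, stops drug, perhaps receives a diuretic, and is back below the threshold at the next scheduled visit would add nothing to the SAP 12.4 count.

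**Working it through.** The plan gives no figure to reproduce, so the check has two parts.

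**1. Tracing one trigger to the table.** A patient meets the rule on a home weight between clinic visits.
- The home weight is in the diary, which is reviewed at the triggered visit but not entered in the eCRF (9.7, 9.10.7).
- No clinic weight is required at that visit (9.1.1, 9.7, 9.10.10, 9.10.11).
- If one is taken anyway, SAP 7 excludes unscheduled measurements by default. SAP 7.3 might admit it, because it selects the measurement closest to the target day within contiguous windows, but a scheduled weight nearer the target would displace it. The two sections are not reconciled.
- The patient is therefore counted only if the gain is still present, or has recurred, at a scheduled clinic weight.

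**2. How often a scheduled clinic weight would catch the gain.**

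Inputs:
- Post-dose clinic weights in the first 8 weeks: Weeks 1, 2, 4, 6 and 8, i.e. Days 7, 14, 28, 42 and 56 (Protocol Table 5).
- Home weights: daily on Days 2-56, i.e. 55 days. The ratio is 5/55 = 9.1%.
- Duration of a gain: not in the documents, so varied.

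Assumptions: the gain starts with equal probability on each day of the stated period, lasts L consecutive days, visits fall on their target days, and no weight from the triggered visit is used.

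A gain starting on day s is caught if some clinic day v satisfies s ≤ v ≤ s + L − 1. Share missed = 1 − (start days caught)/(all start days). The second onset period, Days 2-28, reflects the early timing of risk described in Protocol 5.1.2.1.

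| L (days) | Caught, onset Days 2-56 | Missed | Caught, onset Days 2-28 | Missed |
|---|---|---|---|---|
| 3 | 15/55 | 73% | 9/27 | 67% |
| 5 | 25/55 | 55% | 15/27 | 44% |
| 7 | 34/55 | 38% | 20/27 | 26% |
| 10 | 43/55 | 22% | 23/27 | 15% |
| 14 | 55/55 | 0% | 27/27 | 0% |

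Example for L = 7, onset Days 2-56: start days 2-14, 22-28, 36-42 and 50-56 are caught (13 + 7 + 7 + 7 = 34). Start days 15-21, 29-35 and 43-49 are missed (21), and 21/55 = 38%.

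**Two further mismatches.** SAP 12.4 counts by time point and gives no per-patient count of ever meeting the threshold. It is also not confined to the rule's period: the Week 8 window runs to Day 70 (SAP Table 3), and Weeks 12 and 16 are time points too. Separately, Protocol Table 5 takes both a home and a clinic weight on Day 1, and 9.1.1 does not say which is the reference. The SAP baseline, the last non-missing value before first dose (SAP 7.2), would normally be the clinic one.

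**The case against.** The strongest reply is that no planned analysis is broken. The weight endpoint is change from baseline, and SAP 12.4 describes eCRF weights by time point without claiming to report how often the stop rule was met. That is correct as a reading of the SAP, but it means no planned table reports the frequency of the weight trigger.

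A reader might infer that SAP 12.4 can count nobody who met the rule. The documents do not support this. The rule covers any qualifying gain in the first 8 weeks, and one present at a scheduled clinic weight both meets the rule and is counted.

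A reader might also infer that the triggering weight leaves no record. It does: the diary is reviewed at the triggered visit and at every on-treatment contact. What is missing is its entry in the analysis database.

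Nor is the clinical event necessarily unrecorded. AEs and concomitant medications are collected at unscheduled visits. Protocol 9.1.1 requires a documented fluid-overload assessment before restart and expects diuretic changes made for edema to be reported. SAP 12.1.2 tabulates TEAEs leading to interruption. It would be wrong to say that an AE is recorded only if the investigator finds the change significant: Protocol 11.2.1.1 requires all AEs to be reported regardless of clinical significance, and the significance test in 11.6 is for laboratory and ECG changes.

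These routes stand, but none records that the weight trigger was met. The interruption table needs an AE as the cause. Duration of treatment in SAP 10.2 is last dose minus first dose plus one, which hides an interruption; the dose count falls but gives no reason.

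**Conclusion.** The point holds in a limited form. As written, the plan cannot identify patients whose weight trigger was seen only on home weights between scheduled clinic weights, so the SAP 12.4 count will tend to understate how often the trigger was met.

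The direction follows from the text. The size does not: across durations of 3 to 14 days the illustrative share missed runs from 73% to 0% (67% to 0% for onset in Days 2-28). It depends on a duration the documents do not give, on even onset, and on no weight from the triggered visit being used. None of these percentages should be quoted as an estimate of under-counting in this trial. Short gains are plausible because 9.1.1 itself stops the drug and encourages early diuretic use, but that is a reason for capturing the trigger and does not measure the loss.

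The change is worth making because it improves ascertainment for a primary safety objective at little cost.

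**What to change.** - **eCRF:** for each 9.1.1 trigger, enter the trigger type and date, the triggering weight, the Day 1 reference weight and which scale it came from, and the drug stop and restart dates.
- **Triggered visit:** record a clinic weight, and reconcile Protocol 9.1.1 with 9.7 on what that visit records.
- **SAP 12.4:** add the number and percentage of patients who ever met a 9.1.1 trigger through Week 8, taken from this record. Label the existing table as gains seen at scheduled clinic visits.

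The trigger thresholds and the clinical actions stay as they are. The cost is one eCRF page, a protocol clarification and minor data entry for triggered patients; the scale, the diary and the visit already exist.

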### 9.10.8. Electrocardiograms (ECG)

A 12-lead ECG will be recorded as indicated in Table 5 after the patient has rested for at least 10 minutes in a supine position. The heart rate from the ECG machine should not be used as part of the vital sign measurements.

### 9.10.9. Echocardiogram

An echocardiogram will be recorded as indicated in Table 5 to determine patient eligibility.

### 9.10.10. Vital Sign Measurements

Vital sign measurements include the patient's heart rate (beats/minute taken for at least 15 seconds), respiration rate, and body temperature. Blood pressure should be taken after the patient has rested in a sitting position for at least 5 minutes. The same arm (usually the non-dominant arm) and the appropriate size cuff should be used for each measurement. Vital sign measurements should be taken as indicated in Table 5.

# 9.10.11. Physical Examination

A comprehensive physical examination must be performed by a physician, physician assistant, or registered nurse practitioner as indicated in Table 5 and as documented within the table footnotes. The examination must include the following organ or body system assessments: head, eyes, ears, nose, throat, musculoskeletal, cardiovascular, lymphatic, respiratory, abdomen, skin, extremities, and neurological. Assessments of any specific signs or symptoms reported by the patient must also be performed and documented along with any other findings of note. Clinically significant findings at Screening must be recorded as medical history. Following the examination at Screening, new or changed physical examination findings meeting the definition of an adverse event must be reported as an adverse event. If possible, the same individual should perform each physical examination on a patient during the study.

# 9.10.12. Pregnancy Test

WOCBP (see Section 9.8) will complete a pregnancy test as indicated in Table 5, or at any time if pregnancy is suspected. Negative test results are required on Day 1 before study drug administration. Any patient who becomes pregnant during the study must discontinue taking study drug immediately. See Section 9.8.3 for a description of procedures to be followed in case of pregnancy.

### 9.10.13. Study Drug Administration

Patients should self-administer one capsule from each bottle included in the study drug kit orally once a day beginning on Day 1 through the end of the study, as indicated in Table 5. Each dose of study drug should be administered at approximately the same time each day, preferably in the morning. On days when PK samples are collected, patients must not self-administer study drug. Study staff will administer study drug at the clinic following collection of the first PK sample.

A vomited dose must not be replaced. A double dose (e.g., missed dose from previous day and dose for current day) must not be taken.

# 9.10.14. Study Drug Dispensation and Collection

Study drug will be dispensed to the patient and collected from the patient as indicated in Table 5. The patient will be dispensed one treatment kit at Day 1, Week 2, Week 4, Week 6 (only if baseline ACR >300 mg/g) and Week 8. Dispensed treatment kits from each visit should be returned to the site for collection at the subsequent visit.

### 9.10.15. Telephone Contact

Patients will be contacted by telephone as indicated in Table 5. Patients will be asked about their body weight and other signs of fluid retention, as well as AEs and any changes to concomitant medications. If fluid retention is suspected, the patient must be brought into the clinic and evaluated by the investigator as soon as possible, as detailed in Section 9.1.1.

#### 9.10.16. Adverse Event Collection

Patients will be observed for general appearance, presence of illness or injury, or signs indicative of a concurrent illness as indicated in Table 5. Patients must be instructed to volunteer any information regarding AEs on or after the first dose of study drug or query the patients with an open question regarding any AEs they may be experiencing (e.g., "How have you been feeling since your last visit?"). Any findings are to be documented. Patients must be asked if they have been hospitalized, had any accidents, used any new medications, or changed concomitant medication regimens (including prescription drugs, over-the-counter medications, vitamins, herbal products, and minerals). Responses must be documented in the source documents.

### 9.10.17. Kidney Biopsy

Kidney biopsies will be performed as indicated in Table 5 for patients enrolling in the IgAN or FSGS cohorts to determine patient eligibility. Detailed instructions will be provided in a separate laboratory manual provided to the investigator.

### 9.10.18. Fasting C-Peptide Levels

Fasting C-peptide levels will be assessed as indicated in Table 5 for patients enrolling in the T1D cohort to determine patient eligibility. Detailed instructions will be provided in a separate laboratory manual provided to the investigator.

# 9.10.19. Genetic Testing

Genetic testing for PKD1 mutations for patients enrolling in the ADPKD cohort will be performed as indicated in Table 5 to determine patient eligibility. Detailed instructions will be provided in a separate laboratory manual provided to the investigator

# 9.10.20. Clinical Chemistry

Samples will be collected for the following clinical chemistry analyses as indicated in Table 5: ferritin, creatine kinase (CK), BUN, enzymatic creatinine, eGFR, TBL, direct bilirubin, ALT, AST, ALP, sodium, potassium, calcium, phosphorus, uric acid, total protein, glucose, albumin,

lactate dehydrogenase (LDH), magnesium, chloride, bicarbonate, and GGT. Women of childbearing potential will require a serum pregnancy test (hCG-Qual) at the Screen A visit or at any point in time if a pregnancy is suspected.

#### 9.10.20.1. eGFR

The eGFR value will be calculated by a central laboratory and provided to the investigator by a facsimile report. The eGFR values collected at Screen A and Screen B visits will be averaged to determine eligibility. The two eGFR values used to determine eligibility must have a percent difference ≤ 25%, as determined by the following calculation:

Percent Difference = 
$$|X-Y| / ((X+Y)/2)$$

X=1st eGFR value (Screen A)

 $Y=2^{nd}$  eGFR value (Screen B)

|X-Y| = absolute value of the difference between the two eGFR values

The Chronic Kidney Disease Epidemiology Collaboration (CKD-EPI) equation will be used to calculate eGFR for each patient throughout the study, using the patient's age on the date of consent:

eGFR (mL/min/1.73 m^2) = 
$$141 \times \min(S_{cr}/\kappa, 1)^{\alpha} \times \max(S_{cr}/\kappa, 1)^{-1.209} \times 0.993^{Age} \times 1.018$$
 [if female] × 1.159 [if black]

# 9.10.21. N-Terminal Pro-Brain Natriuretic Peptide (NT-Pro BNP) and Brain Natriuretic Peptide (BNP)

Samples will be collected for NT-Pro BNP and BNP as indicated in Table 5. As recent exercise may affect BNP and NT-Pro BNP levels, patients should be allowed to rest for one hour following arrival at the clinic and prior to obtaining this blood sample. This sample must be taken with the patient in the same position at all appropriate visits, *e.g.*, sitting or semi-recumbent.

Detailed instructions on collection, storage and shipment of the sample will be provided in a separate laboratory manual provided to the investigator.

### 9.10.22. Insulin-Like Growth Factor-1 (IGF-1) and Serum Ketones

Samples will be collected for IGF-1 and serum ketones as indicated in Table 5. Detailed instructions on collection, storage and shipment of the samples will be provided in a separate laboratory manual provided to the investigator.

# 9.10.23. Hematology

Samples will be collected for the following hematology assessments as indicated in Table 5: hematocrit, hemoglobin, hemoglobin A1c, red blood cell (RBC) count, white blood cell (WBC) count, neutrophils, bands (if detected), lymphocytes, monocytes, basophils (if detected), eosinophils (if detected), absolute platelet count, mean corpuscular hemoglobin (MCH), mean corpuscular volume (MCV), and mean corpuscular hemoglobin concentration (MCHC).

[figure not shown]
### 9.10.24. Urinalysis and Microscopy

Samples will be collected for the following urinalysis and microscopy assessments as indicated in Table 5: specific gravity, ketones, pH, protein, blood, glucose, clarity, color, leukocytes, nitrite, bilirubin, and a microscopic examination (if indicated based on laboratory results).

# 9.10.25. Urine Collection for Albumin to Creatinine Ratio (ACR)

Albumin/creatinine ratio will be measured by first morning void spot urine collection as indicated in Table 5. Appropriate containers for the collection will be provided to the patient at the visit prior to the collection.

Patients should be instructed how to properly capture a sample of their first morning void, defined as their first urination after 5 AM. Following Day 1, if a patient presents for a visit and has forgotten to collect (or bring) the urine sample(s) for that visit, they may return within 7 days to submit the sample(s) collected that day.

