#### Methodology:

This multi-center, open-label Phase 2 trial will study the safety, tolerability, and efficacy of bardoxolone methyl in qualified patients with the following rare chronic kidney diseases (CKD): CKD associated with type 1 diabetes (T1D), IgA nephropathy (IgAN), focal segmental glomerulosclerosis (FSGS), and autosomal dominant polycystic kidney disease (ADPKD). Patients will be enrolled in disease specific cohorts within the trial, and effectiveness of bardoxolone methyl in treating CKD will be assessed separately by cohort for each rare CKD.

Patients will receive bardoxolone methyl throughout the study and the maximum bardoxolone methyl dose will be determined by baseline proteinuria status. Patients with macroalbuminuria  $(300 \text{ mg/g} < ACR \le 2500 \text{ mg/g})$  at the Screen B visit will account for up to approximately 50% of patients enrolled within each cohort. Patients with baseline ACR  $\leq$  300 mg/g will be titrated to a maximum dose of 20 mg, and patients with baseline ACR > 300 mg/g will be titrated to a maximum dose of 30 mg. Patients will start with once-daily dosing at 5 mg and will dose-escalate to 10 mg at Week 2, to 20 mg at Week 4, and then to 30 mg at Week 6 (only if baseline ACR >300 mg/g) unless contraindicated clinically and approved by the medical monitor. Dose de-escalation is permitted during the study if indicated clinically, and subsequent dose re-escalation is also permitted to meet the dosing objective of the highest tolerated dose. Please refer to Section 7.3.1 for additional details on dose escalation and dose de-escalation.

All patients in the study will follow the same visit and assessment schedule. Following randomization on Day 1, patients will be scheduled to be assessed during treatment at Weeks 1, 2, 4, 6, 8, and 12, and by telephone contact on Days 3, 10, 21, 31, 38, and 45. Patients will also be scheduled to be assessed at an in-person follow-up visit at Week 16, four weeks after the end of treatment.

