# 10.4. Study Drug Administration

Please refer to Section 9.10.13 for details on study drug administration. Clear instructions will be provided to the patient regarding the number and type of capsules to be ingested at each study drug administration time point listed in Table 5. Patients must be instructed to continue taking study drug once daily up through their Week 12 visit unless: (1) the patient has been otherwise instructed by the investigator or (2) the patient has been formally discontinued from study treatment

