12.7.3. Change from Baseline in ACR

Within each rare CKD cohort, the change from baseline ACR will be summarized for all patients, as well as by baseline ACR category ($ACR \leq 300$, $ACR > 300$). Summaries of ACR will use the geometric mean with 95% confidence intervals instead of the arithmetic mean, and will display ACR results in units of mg/g. Changes from baseline in ACR will be reported as the post-baseline/baseline ratios and will be summarized by geometric means with 95% confidence intervals at each time point.

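### A make-up urine collected 2 to 7 days after the Week 12 visit can be an off-drug ACR that is still reported as Week 12 and paired with an on-drug eGFR

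*Protocol*

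**What the plan says.** **Make-up rule.** Protocol 9.10.25 requires a first-morning void, "defined as their first urination after 5 AM". The make-up provision opens "Following Day 1, if a patient presents for a visit and has forgotten to collect (or bring) the urine sample(s) for that visit" and allows that "they may return within 7 days to submit the sample(s) collected that day". Only Day 1 is outside it, so it covers the ACR visits at Weeks 4, 8, 12 and 16 in Protocol Table 5.

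**End of dosing.** Protocol 10.4: "Patients must be instructed to continue taking study drug once daily up through their Week 12 visit". Table 5 has PK sampling at Week 12 only, and for PK days Protocol 9.10.13 states: "Study staff will administer study drug at the clinic following collection of the first PK sample". Protocol 9.10.14 lists the kits: "The patient will be dispensed one treatment kit at Day 1, Week 2, Week 4, Week 6" (the last for higher baseline ACR only), then Week 8. Table 5 shows drug collected but none dispensed at Week 12. The synopsis describes an "in-person follow-up visit at Week 16, four weeks after the end of treatment".

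**Analysis.** SAP 7.3 and Table 3 assign visits by study day. Days 71 to 98 are Week 12 for everything except ECG, and only Week 16 carries a condition tied to last dose. The exclusions of values taken after drug has stopped (SAP 7.1.3 and 11.1) name eGFR only, and the one in 7.1.3 is limited to patients who do not complete treatment. SAP 12.7.3: "Within each rare CKD cohort, the change from baseline ACR will be summarized for all patients, as well as by baseline ACR category". SAP 12.7.2 forms ln(ACR)/eGFR from the ACR and the eGFR that each lie nearest the target day, with no requirement that they share a date or a treatment status.

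**The concern.** Protocol 5.1.2.6 describes increases in urinary albumin in some treated patients and attributes them to the drug's pharmacology. ACR on treatment is therefore a safety measure of real interest here, and Week 12 is its end-of-treatment reading. At most visits a make-up void is merely late. At Week 12 it can also cross from on drug to off drug.

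If the effect fades after stopping, such values pull the Week 12 ratio toward 1 and shrink the contrast between Week 12 and Week 16. In ln(ACR)/eGFR the mismatch sits inside one patient's value: the eGFR comes from blood drawn at the visit, the ACR from a urine passed days later. This needs no one to stop drug early; it can occur in a patient who has complied with dosing throughout.

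**Working it through.** **1. Which days are possible.** The Week 12 visit is Day 84 ± 3 (Protocol Table 5), and the make-up limit is 7 days.

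| Visit day | Make-up days +2 to +7 | Inside Days 71 to 98? |
|---|---|---|
| 81 | 83 to 88 | yes |
| 84 | 86 to 91 | yes |
| 87 | 89 to 94 | yes |

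Even a visit on Day 98 − 7 = 91 keeps the whole make-up period inside the window. The Week 16 window starts after Day 98, so none of these voids can be Week 16. If the make-up void is the only ACR in the window, it becomes the Week 12 value.

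**2. Drug status.** Let the last dose be given in clinic on visit day V. A first-morning void on V + k comes before any dose that would have been taken that morning, so the doses not taken number k − 1.

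- k = 1: no dose missed; about one dosing interval since the last dose.
- k = 2: one dose missed.
- k = 7: six doses missed.

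A normal Week 12 void is also about one dosing interval after the previous day's dose, because that morning's dose waits for the clinic. The k = 1 void is therefore equivalent to it. Only k = 2 to 7 is at issue.

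**3. Whether a rule catches it.** SAP 7.3 says how to choose when several on-treatment, or several off-treatment, assessments fall in a window. It does not say what to do with a single off-treatment value in the Week 12 window. The eGFR exclusions do not extend to ACR.

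**4. Size.** The documents give neither the share of patients affected nor the speed of reversal, so both are assumptions. Let R be the true on-drug geometric mean ratio, p the share of Week 12 values taken at k = 2 to 7, and f the fraction of the log effect lost by then.

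Observed ratio = R^(1 − p × f)

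| R | p | f | Observed ratio | Rise understated by |
|---|---|---|---|---|
| 1.5 | 5% | 0.25 | 1.5^0.9875 = 1.49 | about 2% |
| 1.5 | 10% | 0.5 | 1.5^0.95 = 1.47 | 6% |
| 1.5 | 20% | 1.0 | 1.5^0.80 = 1.38 | 23% |

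With 1 to 5 of 25 patients affected and f from 0.25 to 1, the summary reads 1.23 to 1.30 for R = 1.3, 1.38 to 1.49 for R = 1.5, and 1.74 to 1.99 for R = 2.0.

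**5. Against sampling error.** The middle case shifts the log ratio by 0.05 × ln 1.5 = 0.020. Assume an SD of log change of 0.4 to 0.8. With n = 25 the 95% half-width is 2.064 × SD/√25 = 0.17 to 0.33, about 8 to 16 times that shift. In the extreme case the shift is 0.20 × ln 1.5 = 0.081, and the half-width is about 2 to 4 times as large. For ln(ACR)/eGFR at an assumed ACR of 450 (ln = 6.1), the mean numerator moves by 0.020/6.1 = 0.3% in the middle case and 0.081/6.1 = 1.3% in the extreme case.

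**The case against.** The best defence is that a short make-up period is an ordinary trade: a slightly late value is better than none. These are safety summaries, the distortion is small beside the sampling error, and nothing in the documents shows that the albumin effect reverses within a week. Protocol 5.1.1 reports part of the eGFR gain retained four weeks after about a year of treatment, so complete loss within seven days is an outer bound and not an expectation. All of that stands. It limits the size but does not justify labelling the value as on-treatment Week 12.

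Several stronger readings are tempting and are not supported:

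- A reader might infer that every Week 12 make-up void is off drug. The next-morning void is not, in substance (step 2). For a patient who collected a void but did not bring it, the rule can also be read as referring to the visit day. That reading cannot apply to a patient who forgot to collect.
- A reader might extend the point to Week 4, where the planned dose steps up. That make-up void is still on treatment, and it is not always reported as Week 4: 28 + 3 + 7 = Day 38, and Days 36 to 38 fall in the Week 6 window.
- A reader might infer that the on-drug albumin effect at the planned maximum dose goes unmeasured. Week 8 also has a scheduled ACR, by which time Protocol Table 4 has patients at their maximum, and a Week 8 make-up void stays on treatment.

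It can also be said that a date rule would be stricter for ACR than for eGFR, since SAP 7.1.3 tolerates some unstated window after last dose. That is a reason to state the tolerance, which the fix does.

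**Conclusion.** The point holds as a minor one. The text allows an ACR taken after about 1 to 6 missed daily doses to stand as a completer's Week 12 value and to be divided by an on-drug eGFR, and no SAP rule prevents or flags it. The exposed analyses are the ACR ratio (SAP 12.2 and 12.7.3) and ln(ACR)/eGFR (SAP 12.7.2). The primary eGFR analysis does not use ACR after baseline and is untouched.

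The likely direction is to understate a drug-related rise in albumin. That rests on the pharmacological explanation in Protocol 5.1.2.6 and on some reversal within days, which is assumed. The size cannot be known from the documents and is probably small, for example 1.47 in place of 1.5.

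The conclusion also rests on dosing ending at the Week 12 visit, as in Protocol 10.4, Table 5 and the timing of Week 16. Protocol 9.10.13, read alone, has dosing run to the end of the study; the two passages must be reconciled.

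**What to change.** In SAP 7.3 and 12.7, compare the urine collection date with the date of last dose:

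1. Do not use an ACR collected more than 1 day after the last dose as the Week 12 on-treatment value, or in Week 12 ln(ACR)/eGFR.
2. Keep next-morning make-up voids.
3. List the excluded values separately, with days since last dose.
4. Show the Week 12 ACR summary with and without them.

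SAP 7.3 already assigns visits by study day, so the collection date is needed anyway, and SAP section 3 allows amendment before database lock. If the rule is applied to all patients, it also removes Week 12 ACRs from those who stopped drug earlier, in line with how 7.1.3 treats their eGFR. The SAP should say whether that is intended.

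The cost is a short wording change and a few Week 12 ACR values lost from the main summary. Running ACR on the urine taken at the visit for urinalysis is not a good substitute. It would set a sample that is not a first-morning void against a baseline built from first-morning voids, and Protocol 9.10.24 does not say that the specimen is suitable.
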